### **3.1.5 Type and Number of Subjects**

Approximately 350 subjects with active moderate-severe RA despite treatment with MTX will be screened (subjects can be rescreened once) to achieve 210 randomised.

### 3.2 Efficacy and Safety Variables

#### 3.2.1 Disease Activity Score (DAS):

The DAS assessment is a derived measurement with differential weighting given to each component.

The DAS28(CRP) and DAS28(ESR) will be calculated at each assessment time point. The components of the DAS28 arthritis assessment include:

- Tender Joint Count 28 (TJC28)
- Swollen Joint Count 28 (SJC28)
- C-reactive protein (CRP) (in mg/L) or Erythrocyte sedimentation rate (ESR) (in mm/hr)
- Patient's Global Assessment of Arthritis Disease Activity (PtGA) (visual analogue scale with values from 0=best to 100=worst)

#### DAS28(CRP)

The DAS28(CRP) score will be calculated using the following formula:

$$\text{DAS28(CRP)} = 0.56 * \sqrt{\text{TJC28}} + 0.28 * \sqrt{\text{SJC28}} + 0.36 * \ln(\text{CRP} + 1) + 0.014 * \text{PtGA} + 0.96.$$

If one of the components is missing at an individual assessment point, the DAS28(CRP) value for that assessment will be set to missing. An alternative imputation method for missing components will be applied as described in Section 4.5.2.

#### DAS28(ESR)

The DAS28(ESR) score will be calculated using the following formula:

$$\text{DAS28(ESR)} = 0.56 * \sqrt{\text{TJC28}} + 0.28 * \sqrt{\text{SJC28}} + 0.7 * \ln(\text{ESR}) + 0.014 * \text{PtGA}$$

If one of the components is missing at an individual assessment point, the DAS28(ESR) value for that assessment will be set to missing. An ESR value of 0 will be substituted with ESR=1 for the calculation of DAS28(ESR).

#### DAS28 Remission

DAS28(CRP) remission is achieved by a DAS28(CRP) value lower than 2.6. Similarly, DAS28(ESR) remission is achieved by a DAS28(ESR) value lower than 2.6. Missing DAS28 values will be considered as not achieving remission.

#### Sustained DAS28(CRP) Remission

Sustained DAS28(CRP) remission is achieved if DAS28(CRP) remission is achieved (i.e. "response" in the Non-Responder imputation [NRI] dataset) at every visit within a period of time

that spans at least 24 weeks (168 days) and includes the Week 52 visit. This is a change from the protocol defined endpoint. If a subject has at most two nonconsecutive visits with missing remission data (“no response” in the NRI dataset due to a missed visit or missing DAS28(CRP) component scores) within the 24 week window and the subject was in remission (“response” in the NRI dataset) for all other visits, then the subject will be considered to have sustained remission. Otherwise, two consecutive visits of missing data or more than two visits of missing data in a 24 week window will disqualify the subject for sustained remission.

Two variables will be determined for each subject (not by visit):

- Subject reached sustained DAS28(CRP) remission (yes/no)
- The duration of sustained DAS28(CRP) remission in weeks.

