#### Rationale

Patient's Assessment of Arthritis Pain, Patient's Global Assessment of Arthritis, Physician's Global Assessment of Arthritis, HAQ-DI, and CRP, ESR were added at Weeks 28, 32, 40, 44, and 48, 12-lead ECG at EW; Spirometry (FEV1, FVC) at EW; DLCO at Weeks 52, 62, and EW.

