### **3.2.2 ACR Response Rates**

The American College of Rheumatology's (ACR) definition for calculating improvement in RA is calculated as a 20% improvement (ACR20) in both tender and swollen joint counts and 20% improvement in 3 of the 5 remaining ACR-core set measures: patient and physician global assessments, patient's assessment of arthritis pain, disability, and an acute-phase reactant (i.e. CRP value). Similarly, ACR50 and ACR70 are calculated with the respective percent improvement. This efficacy measurement will be made at every post-baseline study assessment time point.

The specific components of the ACR Assessments that will be used in this study are:

- Tender/Painful Joint count 68 (TJC68)
- Swollen Joint Count 66 (SJC66)
- Patient's Assessment of Arthritis Pain
- Patient's Global Assessment of Arthritis Disease Activity

- Physician's Global Assessment of Arthritis
- CRP (mg/L)
- Health Assessment Questionnaire – Disability Index (HAQ-DI)

For all visits, if any of the component scores are missing, then those scores will be considered as not having met the criteria for improvement. Therefore, if TJC68 or SJC66 or 3 or more of the 5 remaining ACR-core set measures are missing, ACR20/ ACR50/ ACR70 will each be considered as “no response” in the NRI dataset.

For component scores with missing Baseline values or a Baseline value of 0, the percentage improvement can't be calculated and the component will be considered as not having met the criteria for improvement for all visits. If the baseline value is missing, do not use screening visit data for imputation.

Major clinical response is achieved if ACR70 is achieved (i.e. “response” in the NRI dataset) at every visit within a period of time that spans at least 24 weeks (168 days) and includes the Week 52 visit. This is a change from the protocol defined endpoint. If a subject has at most two nonconsecutive visits with missing ACR70 response data (“no response” in the NRI dataset due to a missed visit or missing ACR component scores) within the 24 week window and the subject had ACR70 response (“response” in the NRI dataset) for all other visits, then the subject will be considered to have achieved major clinical response. Otherwise, two consecutive visits of missing data or more than two visits of missing data in a 24 week window will disqualify the subject for major clinical response.

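### The missing-visit allowance for sustained remission and Major Clinical Response does not exempt Week 52 or the first visit of the window, so less than 24 weeks of observed response can qualify

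*SAP*

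**What the plan says.** For sustained DAS28(CRP) remission, SAP 3.2.1 requires remission at each visit in a period "that spans at least 24 weeks (168 days) and includes the Week 52 visit. This is a change from the protocol defined endpoint". The next sentence sets the allowance: "If a subject has at most two nonconsecutive visits with missing remission data" inside the 24-week window, and remission "for all other visits, then the subject will be considered to have sustained remission". The section then closes the rule: "Otherwise, two consecutive visits of missing data or more than two visits of missing data in a 24 week window will disqualify the subject". Missing here means a missed visit or missing component scores.

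SAP 3.2.2 treats Major Clinical Response in the same way. ACR70 is needed "at every visit within a period of time that spans at least 24 weeks (168 days) and includes the Week 52 visit", followed by the parallel allowance: "If a subject has at most two nonconsecutive visits with missing ACR70 response data".

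Elsewhere the SAP is stricter. Under 4.5.2.1 a visit with missing efficacy data is a treatment failure for binary endpoints, so the allowance is a deliberate exception to non-responder imputation. SAP 3.2.1 also derives a duration of sustained remission in weeks, which 4.9.3.1 says will be summarised.

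**The concern.** The first and last visits of the window are what establish that the response lasted 24 weeks. A gap between two observed responses leaves the span intact. A gap at either end shortens it, and the text does not separate the two cases. Week 52 and the first visit lie inside the window to which the allowance applies, and the stated disqualifiers concern only the number and adjacency of missing visits, not their position.

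The SAP added Week 52 as a recorded change from the protocol, yet the allowance lets that visit be absent. Protocol 4.5 gives the opportunity to assess sustained remission of at least 24 weeks as a reason for dosing for 52 weeks, so what counts as 24 weeks should not depend on how a programmer reads the rule. If Week 52 was missed there is also no visit date from which to check the 168 days or compute the duration.

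A second, narrower problem concerns DAS28(CRP) only. One missing component makes the score missing (SAP 3.2.1), and the allowance covers that case even when the components that were observed already rule out remission.

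**Working it through.** **Inputs**
- Required span: at least 24 weeks, 168 days, Week 52 included (SAP 3.2.1 and 3.2.2).
- Visit days from SAP Table 1: Week 28 = Day 197, Week 32 = Day 225, Week 48 = Day 337, Week 52 = Day 365.
- Spacing: the joint-count row of SAP Table 1 reads as every 4 weeks from Week 12 to Week 48, then Week 52. The Amendment 01 entry in Protocol Appendix 12.9 agrees: "CRP, ESR were added at Weeks 28, 32, 40, 44, and 48".
- DAS28(CRP) formula: SAP 3.2.1.

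**The plan's own figure.** 24 × 7 = 168 days, and 365 − 197 = 168 days. The shortest nominal window is therefore Weeks 28 to 52, with seven efficacy visits: Weeks 28, 32, 36, 40, 44, 48 and 52.

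**Patterns that qualify as written.** None missing: 1. One missing: 7. Two missing and not adjacent: 21 pairs less 6 adjacent pairs = 15. Total 1 + 7 + 15 = 23.

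| Visits missing at the ends | Patterns | Observed span |
|---|---|---|
| Neither Week 28 nor Week 52 | 12 | 24 weeks |
| Week 28 only | 5 | Weeks 32 to 52 = 20 weeks |
| Week 52 only | 5 | Weeks 28 to 48 = 337 − 197 = 140 days = 20 weeks |
| Both | 1 | Weeks 32 to 48 = 337 − 225 = 112 days = 16 weeks |

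In 11 of the 23 patterns the observed span is below 24 weeks, and in 6 of them Week 52 itself is missing. The worst case is 112/168, two thirds of the requirement. These are counts of patterns, not probabilities.

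**Longer windows.** If the window starts at Week 24 (eight visits), 30 patterns qualify: 17 have 28 weeks observed, 12 have 24 weeks, and 1 (Weeks 24 and 52 missing) has 20 weeks. A subject in remission from Week 20 who lacks only Week 52 has Weeks 20 to 48, or 28 weeks, observed. The short spans therefore arise mainly when the window cannot start before Week 28, for example because Week 24 was an observed non-response.

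**Sensitivity to the schedule.** The Time and Events tables are partly broken in the text read here. With visits every 2 weeks, the worst case from Week 28 would be 20 weeks instead of 16.

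**Component case, DAS28(CRP) only.** Every component term in the formula is zero or positive, so the tender joint term plus the constant is a lower bound. For TJC28 = 10: 0.56 × √10 + 0.96 = 1.771 + 0.96 = 2.731. For TJC28 = 9: 0.56 × 3 + 0.96 = 2.64. Both exceed 2.6 whatever the CRP, yet with CRP lost the visit is classed as missing and can be forgiven.

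**Effect of the fix.** With both ends required to be observed responses, the 12 patterns in the first row remain, all with 24 weeks observed. Requiring only Week 52 leaves 17 patterns with a minimum of 20 weeks.

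**The case against.** The best defence is that including the Week 52 visit implies a visit that took place. A missed visit has no date, so a 168-day span cannot be computed to it. That reading is possible, but it is not written. The allowance relaxes the every-visit requirement for all visits in the window alike, and even on this reading a Week 52 visit that was attended but lacked CRP would pass.

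Several limits on the point do stand, and they rule out stronger conclusions that a reader might draw:

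- *That 16 weeks will commonly count as 24.* It is one pattern of 23 and needs a window starting at Week 28. The documents give no frequency for missing Week 52 data.
- *That the endpoint is necessarily overstated.* True status at a forgiven visit is unknown, and counting every missing visit as failure could err the other way. The direction is certain only relative to the SAP's own requirement of response at every visit.
- *That dropouts and rescued subjects become sustained responders.* The allowance names missed visits and missing components. SAP 4.5.2.1 lists early withdrawal, rescue and corticosteroid failures as separate grounds for failure.
- *That one lost component also makes an ACR70 visit missing.* It need not. SAP 3.2.2 counts a missing component as not improved, so the visit can still be a response. The component argument is confined to DAS28(CRP).
- *That the treatment comparison is biased.* The rule is identical in all arms, and nothing in the documents shows a difference between them.

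**Conclusion.** The point holds as a gap in two endpoint definitions. As written, the allowance reaches the visits that define the span, so on the minimum window a subject can qualify on 20 weeks of observed response, or at worst 16, against a stated 24. This rests on nominal visit days, 4-weekly efficacy visits, and a literal reading in which the allowance applies throughout the window. Relative to the stated definition it can only add responders, by a number that the documents do not allow one to estimate.

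Both endpoints are exploratory (SAP section 2) and are analysed only at the final analysis (SAP 4.9.3). The primary Week 24 remission analysis and the interim decision rules are untouched. The matter is worth settling before the final analysis because two competent programmers could code the rule differently and report different proportions.

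**What to change.** In SAP 3.2.1 and 3.2.2, state that response must be observed at Week 52 and at the first visit of the window of at least 24 weeks, and that the allowance for up to two nonconsecutive missing visits applies only to visits strictly between them. This also gives the 168-day check and the duration variable a dated start and end.

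In SAP 3.2.1 only, add that a visit is not forgiven when its observed components alone give a DAS28(CRP) of 2.6 or more.

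The cost is a few sentences of SAP wording and the matching derivation code, with no new data collection. The downside is that the reported proportions may be slightly lower, since a subject who truly responded but lacks data at an end visit would no longer count unless another qualifying window exists. If the team wants to keep the lenient rule, it could be reported alongside as a sensitivity analysis.

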### Categorical DAS28 Response

DAS28(CRP) and DAS28(ESR) scores will each be categorised using EULAR response criteria. Response at a given time point is defined based on the combination of current DAS28 score and the improvement in the current DAS28 score relative to baseline. The definition of no response, moderate response and good response is captured in the following table:

**Table 2 EULAR Response Criteria**

Current DAS28	DAS28 decrease from baseline value		
	>1.2	>0.6 to $\leq$ 1.2	$\leq$ 0.6
$\leq$ 3.2	Good response	Moderate response	No response
> 3.2 to $\leq$ 5.1	Moderate response	Moderate response	No response
> 5.1	Moderate response	No response	No response

If the post-baseline DAS28(CRP) or DAS28(ESR) score is missing, then the corresponding EULAR category will be missing.

### **3.2.2 ACR Response Rates**

The American College of Rheumatology's (ACR) definition for calculating improvement in RA is calculated as a 20% improvement (ACR20) in both tender and swollen joint counts and 20% improvement in 3 of the 5 remaining ACR-core set measures: patient and physician global assessments, patient's assessment of arthritis pain, disability, and an acute-phase reactant (i.e. CRP value). Similarly, ACR50 and ACR70 are calculated with the respective percent improvement. This efficacy measurement will be made at every post-baseline study assessment time point.

The specific components of the ACR Assessments that will be used in this study are:

- Tender/Painful Joint count 68 (TJC68)
- Swollen Joint Count 66 (SJC66)
- Patient's Assessment of Arthritis Pain
- Patient's Global Assessment of Arthritis Disease Activity

- Physician's Global Assessment of Arthritis
- CRP (mg/L)
- Health Assessment Questionnaire – Disability Index (HAQ-DI)

For all visits, if any of the component scores are missing, then those scores will be considered as not having met the criteria for improvement. Therefore, if TJC68 or SJC66 or 3 or more of the 5 remaining ACR-core set measures are missing, ACR20/ ACR50/ ACR70 will each be considered as “no response” in the NRI dataset.

For component scores with missing Baseline values or a Baseline value of 0, the percentage improvement can't be calculated and the component will be considered as not having met the criteria for improvement for all visits. If the baseline value is missing, do not use screening visit data for imputation.

Major clinical response is achieved if ACR70 is achieved (i.e. “response” in the NRI dataset) at every visit within a period of time that spans at least 24 weeks (168 days) and includes the Week 52 visit. This is a change from the protocol defined endpoint. If a subject has at most two nonconsecutive visits with missing ACR70 response data (“no response” in the NRI dataset due to a missed visit or missing ACR component scores) within the 24 week window and the subject had ACR70 response (“response” in the NRI dataset) for all other visits, then the subject will be considered to have achieved major clinical response. Otherwise, two consecutive visits of missing data or more than two visits of missing data in a 24 week window will disqualify the subject for major clinical response.

### **3.2.3 Swollen and Tender/Painful Joint Count**

Four different scores will be calculated to evaluate swelling and tenderness of joints. TJC28 and SJC28 will take 28 joints into account, SJC66 and TJC68 will use 66 and 68 joints, respectively.

The assessment for swelling is the total number of joints with a present swelling and ranges from 0 to 28 for SJC28 and 0 to 66 for SJC66.

The assessment for tenderness is the total number of joints with a present tenderness and ranges from 0 to 28 for TJC28 and 0 to 68 for TJC68.

The following 28 joints will be taken into account for TJC28 and SJC28: Shoulder (2 joints), Knee (2), Elbow (2), Wrist (2), Fingers (PIP, MCP: 20).

Additionally the following joints will be taken into account for SJC66/TJC68: Temporomandibular (2), Sternoclavicular (2), Acromioclavicular (2), Fingers (DIP: 8), Ankle (2), Tarsus (2), Toes (PIP, MTP: 20), Hip (2, only for TJC). Artificial, ankylosed and missing joints are excluded from swelling and tenderness assessment.

If there are missing observations for tender or swollen joints then the remaining observations will be assessed and weighted by dividing the number presented by number of non-missing and by

multiplying by 28/66/68 for the joint count. No imputations for individual joints will be done. If a joint is not evaluable at Baseline, then that joint is set to missing throughout the study.

If data for more than 50% of the joints are missing at the time of a given assessment, then the total count will be set to missing for that visit.

Observed joint states will be listed without any modification for every subject and visit.

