### **7.3.1.1. Replaced or Fused Joints**

Replaced or fused joint will not be included in joint evaluations. The reason for absence of the evaluations of those joints must be recorded.

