### 3.2.9 Index- and Boolean-based ACR/EULAR Remission Rates

Boolean-based remission ([Felson, 2011](#)) is achieved if all of the following requirements are met at the same time:

- $TJC68 \leq 1$
- $SJC66 \leq 1$
- $CRP \leq 1\text{mg/dl}$
- $PtGA \leq 10$

If one of the components is missing at an individual assessment point, Boolean-based remission for that assessment will be set to missing.

Index-based remission is achieved if the following requirement is met:

- $SDAI \leq 3.3$

If the SDAI value is missing at an individual assessment point, Index-based remission for that assessment will be set to missing.

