For binary endpoints with repeated measures over time, Generalized Estimating Equations (GEE) methodology will be used to take correlation among subject-level responses over time into account. The model will include data from all assessment points from Week 1 to Week 62. Due to only few expected subjects with remission in some randomised treatment groups (especially placebo) only standard errors and resulting confidence intervals will be adjusted. To this end an independent working correlation structure will be assumed and standard errors will be calculated based on the empirical sandwich covariance estimate (default setting for PROC GENMOD in SAS) (Stokes, Davis, & Koch, 2012).

For the primary analysis of DAS28(CRP) remission at Week 24, the GEE model will include terms for randomised treatment group, baseline DAS28(CRP), visit and interaction terms for treatment group-by-visit and baseline-by-visit. A sensitivity analysis including covariates age, gender, weight and disease duration (<2 years,  $\geq 2$  years) will be considered by adding covariate terms to the repeated measures model one at a time along with the covariate-by-treatment group interaction term. If the interaction term is not significant at  $\alpha=0.10$  it will be removed from the model. Likewise, if the covariate term is not significant at  $\alpha=0.10$  it will be removed from the model. Other covariates will be tested in a similar manner.

Survival analyses (time to event analyses) will be conducted for the final analysis using Kaplan-Meier methods, comparing each GSK3196165 dose to placebo. Between-group differences will be analysed using the log-rank statistic. Median time to remission will be presented for each randomised treatment group. Kaplan-Meier plots of the time to remission will be presented. Subjects who withdraw from the study are censored at the time of withdrawal. All other subjects are censored at the end of the study.

In addition to summaries of the individual components of composite endpoints, numbers and percentages of subjects meeting the following criteria will be presented:

- TJC68  $\leq 1$
- SJC66  $\leq 1$
- CRP  $\leq 1\text{mg/dl}$
- PtGA  $\leq 10$
- SDAI  $\leq 3.3$

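### Rescaling the joint counts turns the one-joint allowance in Boolean remission into zero when a joint belonging to that count is not evaluable

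*SAP*

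**What the plan says.** SAP 3.2.3 derives four counts: TJC28, SJC28, SJC66 and TJC68. It states that "Artificial, ankylosed and missing joints are excluded from swelling and tenderness assessment", in line with Protocol 7.3.1.1: "Replaced or fused joint will not be included in joint evaluations". For incomplete joint data, "the remaining observations will be assessed and weighted by dividing the number presented by number of non-missing" joints and then "multiplying by 28/66/68 for the joint count. No imputations for individual joints will be done". The exclusion can be permanent: "If a joint is not evaluable at Baseline, then that joint is set to missing throughout the study". There is an upper limit: a visit has no usable count once over half of its joints lack data. The two hips enter the tender count only.

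SAP 3.2.9 defines Boolean remission, which "is achieved if all of the following requirements are met at the same time": TJC68 ≤1, SJC66 ≤1, CRP ≤1 mg/dl and PtGA ≤10. SAP 4.9.2.2 uses the same two joint limits again as separate component cut-offs, for which "numbers and percentages of subjects meeting the following criteria will be presented". Neither section says whether the limits apply to the weighted count, a rounded count or the number of joints actually affected. The variable names are those of the weighted counts in 3.2.3. The decimal-place rules in SAP 4.2 concern reporting, not derivation.

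**The concern.** A limit of one joint is meant to let a subject with a single tender or swollen joint qualify. The weighting factor exceeds 1 as soon as one joint of the count is missing, so that subject's score moves just above 1 and the criterion fails. The outcome is a computed non-remission, not a missing value, so no summary of missing data would show it.

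The situation is foreseeable. Protocol 7.3.1.1 provides for replaced and fused joints. The exclusion criteria in Protocol 5.2 rule out an infected prosthesis still in place and recent or planned surgery, but not an older replacement or fusion. The rule also applies at any single visit where one joint goes unassessed. Boolean remission is listed among the major secondary efficacy endpoints at all assessment timepoints. With 35 subjects per arm, one reclassified subject moves an arm's rate by 1/35 = 2.9 percentage points.

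**Working it through.** **Inputs.** The joint list, weighting rule and 50% limit come from SAP 3.2.3. The limits come from SAP 3.2.9 and 4.9.2.2. The planned remission rates (33% active, 3% placebo) and 35 per arm come from SAP 4.13.1.

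**Reproducing the multipliers.** Shoulders, knees, elbows, wrists and the listed finger joints: 2+2+2+2+20 = 28. Further joints in both large counts: 2+2+2+8+2+2+20 = 38, and 28+38 = 66. Adding two hips for tenderness gives 68. These match the SAP.

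**Weighted count.** With *a* affected joints, *m* missing joints and full count *F*: weighted count = a × F/(F − m). For a = 1:

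| Missing joints in that count | TJC68 | SJC66 | ≤1 met? |
|---|---|---|---|
| 0 | 68/68 = 1.0000 | 66/66 = 1.0000 | yes |
| 1 | 68/67 = 1.0149 | 66/65 = 1.0154 | no |
| 2 | 68/66 = 1.0303 | 66/64 = 1.0313 | no |
| 10 | 68/58 = 1.1724 | 66/56 = 1.1786 | no |
| half | 68/34 = 2.0 | 66/33 = 2.0 | no |

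With a = 0 the weighted count is 0 in every row. The effect is therefore confined to subjects with exactly one affected joint in a count that has a missing joint.

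**Hips.** If one hip is the only excluded joint, SJC66 still has 66 of 66 joints and one swollen joint scores 1.0000, which passes. One tender joint scores 68/67 = 1.0149, which fails.

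**Effect of rounding.** Rounded to the nearest integer, one affected joint still scores 1 with up to 22 of 68 joints missing (68/46 = 1.478) or up to 21 of 66 (66/45 = 1.467). The next steps, 68/45 = 1.511 and 66/44 = 1.5, round to 2.

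**Primary endpoint.** DAS28(CRP) has no whole-number joint limit. With one affected and one missing joint of 28, weighting adds 0.56 × (√(28/27) − 1) = 0.010 for a tender joint and 0.28 × (√(28/27) − 1) = 0.005 for a swollen one.

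**How many subjects.** The documents do not say, so this is an illustration on three assumptions:
- 5% to 20% of 210 subjects have a missing counted joint: 10.5 to 42.
- The planned DAS28(CRP) remission rates stand in for otherwise meeting the Boolean criteria: (5 × 33% + 3%)/6 = 28%.
- 10% to 40% of those subjects have exactly one affected joint in the affected count.

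Low end: 10.5 × 0.28 × 0.10 = 0.3. High end: 42 × 0.28 × 0.40 = 4.7. That is roughly 0.3 to 5 subjects across six arms.

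**The case against.** The strongest reply is that little depends on this. Boolean remission is one of many secondary endpoints. It plays no part in the primary analysis or in the stopping and arm-dropping criteria of SAP Table 4, and the component cut-offs in 4.9.2.2 are descriptive. The SAP never says that the limits refer to raw counts, so calling the affected subjects true remitters presumes an answer. A programmer might also round. All of that limits the size of the problem. It does not resolve it: the SAP states no rounding, and two programmers could derive different remission rates from the same data.

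Four stronger readings are tempting, and the documents do not support them:
- **Both limits fail for every subject with an excluded joint.** Hips are outside SJC66, so an excluded hip affects only the tender limit.
- **Some 10 to 42 of 210 subjects are misclassified.** On an assumed 5% to 20%, that is the number held to a stricter limit. Misclassification also needs exactly one affected joint in the relevant count, no more than one in the other, and both the CRP and PtGA criteria met at the same visit.
- **The treatment comparison is biased towards one arm.** The rule uses no treatment information, and joints not evaluable at baseline are fixed before dosing. If the same share of remitters is missed in each arm, differences shrink slightly in proportion.
- **The comparison by disease duration is distorted.** Excluded joints may be commoner in longer disease, but no figure in the documents shows it. Table 6 marks Boolean remission for subgroup tables, while the list in SAP 4.9.1.6 omits it, and no formal subgroup test of it is specified.

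**Conclusion.** The point holds in limited form. Read literally, SAP 3.2.3 combined with 3.2.9 and 4.9.2.2 changes an allowance of one joint into zero for any count in which at least one of its own joints is missing. This is a stated rule with an unintended result on a listed major secondary endpoint, and nothing elsewhere in either document corrects it.

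The arithmetic is certain, provided that the weighted counts are used unrounded. The number of subjects affected is not known. The illustrative range rests entirely on the assumed shares, and a small number is the likely case. The consequence is a slight lowering of absolute Boolean remission rates in all arms. The largest shift found for DAS28(CRP), about 0.01 in the one-joint case, leaves the primary endpoint essentially unaffected. The correction is worth making because it is cheap and removes a choice that would otherwise be made in programming.

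**What to change.** In SAP 3.2.9, and for the component cut-offs in 4.9.2.2, specify one of two rules before the Week 24 unblinding:

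1. The TJC68 ≤1 and SJC66 ≤1 limits use the unweighted number of affected evaluable joints, set to missing if more than 50% of the joints are missing.
2. The limits use the weighted count rounded to the nearest integer.

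Keep the weighted counts for DAS28, SDAI, CDAI, ACR response and the continuous summaries.

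The first rule is the simpler, but it is lenient when many joints are unassessed. A subject with 33 of 66 joints missing and one swollen joint would pass, although the weighted count is 2. The second rule avoids this and still restores the one-joint allowance when few joints are missing.

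Either rule costs one sentence and one derived variable. No new data are needed, because SAP 3.2.3 already has the observed joint states listed without changes for every subject and visit.
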